3.2. Safety Assessments

Continuous assessment of study-related adverse events (AEs) will be collected. An independent Data and Safety Monitoring Board (DSMB) will review events.

4. Study Design

LOFT-HF is a Phase 3, multi-center, randomized, double-blind, sham-controlled outcomes trial with parallel group design, with patients randomized to either control (optimal GDMT plus sham NOXT) or active treatment (optimal GDMT plus NOXT) in a 1:1 ratio.

4.1. Enrollment

Participants will be recruited from outpatient clinics and inpatient clinical settings (see Section 10 for Recruitment Plan). To enrich the study population for morbid and mortal events, we will enroll at least 30% of patients with poor prognostic markers, such as HF hospitalization within the prior year and/or elevated outpatient BNP or NTproBNP level. Those screened from inpatient settings for decompensated HF and without a previous clinical sleep study within the past 12 months can be screened prior to hospital discharge, when in a stable, optimized health, using the research PSG device. Baseline morbidity measurements will be continuously monitored to ensure that the study enrolls a high morbidity group (recruitment strategies will be changed if departures from expectation are observed.)

Patients will be screened for SDB, as detailed in Section 8.2. Screening will be documented in a screening log. Based on the assumptions detailed in the sample size calculation (see Section 11.2 for Sample Size Calculation), including a 35% screen positive rate by sleep study, a total of 2,450 patients will need to be screened with sleep studies to randomize a total of 858 patients (429 per arm) eligible patients.

Written informed consent must be obtained prior to any study related procedure. Before final enrolment, all eligibility criteria must be checked by filling in the inclusion/exclusion criteria case report form (CRF) and entered and verified into a secure study web portal.

4.2. Start-Up Phase

There will be a 3-month start-up phase with a limited number of 10 centers participating to

randomize the first 20 patients. At the end of the start-up phase there will be a feasibility-check performed by the Steering Committee and the study sponsor, the National Heart, Lung, and Blood Institute (NHLBI). The Steering Committee, with input from the NHLBI, will decide on the need for changes of study procedures and the need for amendments of the study protocol, if required.

4.3. Study duration

Following the start-up phase, the total study duration is expected to be 4.5 years. Patients will be followed up on average for a period of about 2.49 years. All patients will be followed, until the last patient randomized completes 6 months of follow up. Thus, minimum follow up time will be 6 months, and maximum follow up is anticipated to be about 4.5 years. With a randomization rate of 0.35 patients per center per month, 838 patients will be randomized over approximately 54 months of enrollment (although this period may be extended based on COVID-19 pandemic-related enrollment delays). Enrollment contingencies are planned, should the actual randomization rate be higher or lower than that assumed (see Section 10.4.3).

5. Selection and withdrawal of patients

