	
Quality of Life and Symptoms
 
 • Change in HF disease-specific quality of life, assessed by Kansas City Cardiomyopathy Questionnaire (KCCQ) • Change in generic-quality of life, assessed by the EQ-5D • Change in depressive symptoms assessed by the PHQ-8 • Change in sleep symptoms and sleep related daytime impairment (including fatigue), assessed by the PROMIS Sleep Disturbance and Sleep Related Impairment Questionnaires 
Functional Status
 
 • Change in NYHA Functional Class Ranking 
Secondary morbidity and mortality endpoints will be measured over the full duration of study follow up. Quality of life, symptoms, and functional status endpoints will be measured at baseline and at 6 and 12 months follow up.

Safety Assessments	Continuous assessment of study-related adverse events (AEs) will be collected.
Scheduled follow up	
Patients will be followed up on average for a period of about 2.5 years. All patients will be followed, until the last patient randomized completes 6 months of follow up. Thus, minimum follow up time will be 6 months, and maximum follow up is anticipated to be about 4.5 years, assuming that the enrolment accrual pattern is uniform across and completed over 3.5 years.
 
In-clinic or remote study visits will occur at Screening/Consent, Baseline, 6 months, and 12 months. Telephone follow-up will occur at 1 month, 3 months, 9 months, 18 months, and then every 6 months after that, until the last participant completes the study. There will be a telephone assessment for each patient at the end of the study, for final ascertainment of mortal and morbid events.
 
Prior the De-briefing Visit, a follow-up in home sleep study will be performed. At the De-briefing Visit the coordinator will review the baseline and follow-up sleep study results, reveal the participant's treatment arm and provide letters for continuity of care.

Independent Committees	
An independent CEC will adjudicate all outcomes associated with the primary and secondary mortality and morbidity endpoints.
 
An Independent Data and Safety Monitoring Board (DSMB) will monitor all efficacy and safety outcomes (including study-related AEs), but will be able to recommend early termination of the trial only for significant excess mortality in the treatment group or for overwhelming evidence of patient benefit or harm.

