11.1. Description of Study

LOFT-HF is a Phase 3, multicenter, randomized, double-blind, sham-controlled outcomes trial with parallel group design, with patients randomized to either control (optimal guideline based medical treatment [GDMT] plus sham NOXT) or active treatment (optimal GDMT plus NOXT)

in a 1:1 ratio. The primary objective is to evaluate the long-term effects of NOXT on the mortality and morbidity of patients with stable heart failure with reduced ejection fraction (HFrEF), already receiving optimal GDMT who have central sleep apnea (CSA). The secondary objectives are to evaluate patient-reported outcomes (disease-specific and generic quality of life); disease-specific mortality; and cardiovascular events. Subgroup analyses are planned to identify which patients treated with NOXT benefit most based on physiological endotypic traits. Adults, ages 21 years and older, with HFrEF and CSA who meet study eligibility criteria, will be recruited from approximately 50 well-established cardiovascular medicine/sleep centers, and further evaluated with sleep studies to identify the presence of CSA. It is anticipated, based on the literature and our experience conducting similar screening, that about 35% of participants will be eligible after PSG. Approximately 2,450 patients will be recruited to undergo PSGs to randomize a total of 858 patients (429 per arm). Participants will undergo standardized assessments including anthropometry, blood pressure, and questionnaires at baseline and at 6 and 12 month follow-up in-person or remote visits. Telephone calls will be conducted at months 1, 3, 9, and every 6 months after the 12 month visit until the last participant has completed his 12-month visit. Adverse events, hospitalizations and vital status will be collected over the entire intervention period. Given a 3.5 accrual period, mean follow-up time is estimated at 2.5 years (max 4.5 years).

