11.3. Sample Size Calculation

[figure not shown]
We hypothesize a 20% reduction in the 1-year composite event rate, which is high enough to change practice. This effect is within the range of that observed across intervention studies (ranging from 35% for cardiac resynchronization therapy and beta blockers to 15% to 25% for other medications [47,48]). We anticipate a 1-year event rate of 40% in the control group based on the HF literature showing that patients with advanced HF will experience annual morbidity and mortality event rates of approximately 40% or greater (71,72), especially in the setting of co-morbid CSA (18,19). As described in the CCC application and Protocol Draft, several design strategies will be employed to enrich the risk of the enrolled patients. We will not use a run-in design that would select samples with better prognosis.

A total sample of 858 subjects (429 in each arm) achieves 88% power at a 5% significance level to detect a hazard ratio (HR) of 0.755 when the 1-year event rate in the control group is 40%, using a two-sided logrank test. We assume that an accrual period of 4.5 years with a slow ramp up until the end of May 2020, then uniform across the remaining recruitment period until the end of January 2024, and that the study will last until the last enrolled subject completes six-month follow-up. We further assume that the drop-out rate and cross-over rate during the study period are 10% and 5% respectively for both treatment groups.

Conservatively assuming that 35% will screen positive will require screening a total of 2,450 subjects.

We performed sensitivity analyses for power analysis based on varying assumptions of effect sizes (HR=0.72, 0.755, and 0.78) and 1-year event rates in the control group (30%, 35%, and

40%), assuming the same rates of losses to follow-up and cross-over. As shown in the Figure, the proposed sample size achieves over 80% power for most of these settings.

Power for varying effect sizes and 1-year control event rate (1-Survival).

AT=Accrual Time (in Months); T=Total Time (in months).

Our sample size also provides adequate power for key secondary endpoints. Using two-sided tests at 5% significance level, a sample size of 858 provides 80% power to detect 0.2 SD difference in means for a continuous endpoint using a two-sample t-test; to detect a 35%, 23%, and 16% reduction in risks when the risk in the control group is 20%, 40% and 60% for a binary outcome using a Z-test with pooled variance.

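### The stated 4.5-year study duration and maximum follow-up do not follow from the protocol's own accrual periods and closing rules; the power calculation itself is sound

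*Combined protocol and SAP*

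**What the plan says.** The timeline appears in several places in the combined protocol and SAP.

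- **Section 4.3.** "Following the start-up phase, the total study duration is expected to be 4.5 years". Enrollment: "838 patients will be randomized over approximately 54 months of enrollment". Closing rule: "All patients will be followed, until the last patient randomized completes 6 months of follow up". Also: "maximum follow up is anticipated to be about 4.5 years" and "Patients will be followed up on average for a period of about 2.49 years".
- **Synopsis, Scheduled follow up.** Minimum follow-up is 6 months, the mean is about 2.5 years, and "maximum follow up is anticipated to be about 4.5 years, assuming that the enrolment accrual pattern is uniform across and completed over 3.5 years".
- **Section 11.1.** Telephone follow-up runs to the last participant's 12-month visit. "Given a 3.5 accrual period, mean follow-up time is estimated at 2.5 years (max 4.5 years".
- **Section 10.4.2.** Milestones within 54 months: 215, 429, 644 and 858 patients in January 2021, 2022, 2023 and 2024.
- **Section 11.2.5, accrual table.** The original design ends accrual on 31 January 2023 with 12 further months (mean 2.75 years, power 90.2%). The revised design ends accrual on 31 January 2024 with 6 further months (mean 2.49 years, power 87.9%). The same section expects 520 events.
- **Section 11.3.** "We assume that an accrual period of 4.5 years with a slow ramp up until the end of May 2020", then uniform accrual to the end of January 2024, with a close 6 months after the last patient enters.
- **Section 8.3.** Follow-up stops on 15 December 2021.

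**The concern.** Duration, accrual and closing rule are not independent: any two fix the third. In Section 4.3 the stated duration equals the enrollment period alone, so the 6-month minimum has no room. The synopsis and Section 11.1 each combine a different accrual period and closing rule, yet both give 4.5 years as the maximum.

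These figures determine the event count, the close-out date, device supply and the longest time a participant can expect to be on study. Someone planning from Section 4.3, the synopsis, Section 11.1 or Section 11.3 would reach different answers, and the text does not say which one governs.

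**Working it through.** **Step 1. Durations from each section's own inputs.** Maximum = accrual + closing period. For uniform accrual, mean = accrual/2 + closing period.

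- Section 4.3: 54 + 6 = 60 months = 5.0 years (stated 4.5). Patients randomized in start-up would be followed slightly longer.
- Synopsis: maximum 42 + 6 = 48 months = 4.0 years (stated 4.5); mean 21 + 6 = 27 months = 2.25 years (stated about 2.5).
- Section 11.1: maximum 42 + 12 = 54 months = 4.5 years (agrees); mean 21 + 12 = 33 months = 2.75 years (stated 2.5).

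The Section 11.1 sum is the original column of the Section 11.2.5 table, which is probably where 4.5 years comes from.

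**Step 2. Reproduce the stated 2.49 years, 520 events and 87.9%.** Inputs from Sections 11.2.5 and 11.3: 429 per arm, two-sided 5% logrank test, one-year control event rate 40%, 20% relative reduction, 10% drop-out and 5% cross-over in each arm over the study.

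Hazards per year: control −ln(0.60) = 0.511; active −ln(0.68) = 0.386; ratio 0.755.

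Accrual: 10 ramp-up months (August 2019 to May 2020), then 44 uniform months to January 2024. The number randomized in ramp-up is not stated, so it is an assumption. The Section 10.4.2 milestones imply 858 − 44 × (214.5/12) = 71.5. A count of 60 reproduces the stated mean: mean entry (60 × 5 + 798 × 32)/858 = 30.1 months, and 60 − 30.1 = 29.9 months = 2.49 years. I take 20 as a low bound and fully uniform accrual as a high bound.

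A Lakatos-type logrank calculation gives:

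| In ramp-up | Close at month 60: mean, events, power | Close at month 54: mean, events, power |
|---|---|---|
| 20 | 2.39 y, 513, 87.5% | 1.89 y, 432, 81.5% |
| 60 | 2.49 y, 523, 88.1% | 1.99 y, 444, 82.5% |
| about 72 | 2.52 y, 525, 88.2% | 2.02 y, 448, 82.8% |
| uniform 54 months | 2.75 y, 547, 89.4% | 2.25 y, 475, 84.8% |

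The 60-month column matches the stated figures. The same method gives 90.1% for the original 42 + 12 design (stated 90.2%), 89.9% for 54 + 9 (stated 89.8%) and 91.3% for 54 + 12 (stated 90.4%).

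**Step 3. What 4.5 years would mean if enforced.** With 54-month accrual, closing at month 54 leaves no follow-up after the last randomization. Power is about 82.5% (81.5 to 84.8%) with about 430 to 475 events, a loss of roughly 5 to 6 points. If drop-out and cross-over are instead taken to accumulate over mean follow-up, the 60-row gives 85.9% at month 60 and 79.3% at month 54. That reading fits the stated 87.9% less well, and the loss is of similar size.

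With 3.5-year accrual, a 4.5-year study is the original design, at about 90%. The synopsis taken literally (42 + 6 months) gives about 86% and 496 events.

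**Step 4. A second reconciliation.** At 0.35 patients per center per month (Section 4.3) and 50 centers (Section 10.4.3), 838/(50 × 0.35) = 47.9 months. Uniform accrual over 48 months plus 6 gives 54 months = 4.5 years, mean 24 + 6 = 30 months = 2.50 years, about 523 events and 88.0% power.

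**The case against.** The strongest reply is that nothing in the design is at risk. The 6-month closing rule is explicit in the synopsis and in Sections 4.3 and 11.3, and Section 8.4 ties the De-briefing Visit to the final participant's 6-month visit. The 4.5 years is only an expectation, and a wrong forecast does not override a stated rule. The power was computed on the 60-month timeline. All of this stands.

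A reader might infer that the trial will close at the last randomization and is therefore underpowered. The documents do not support that. No section sets such a close, the stated power assumes the extra 6 months, and under the synopsis's 3.5-year accrual a 4.5-year study would leave 12 months after the last entry.

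A second reply is that 4.5 years may be correct and 54 months the slip, as Step 4 shows. This is possible, and it would also explain the stated mean. But it needs all 50 centers recruiting at the full rate from the first month, and it contradicts the 54-month milestones in Section 10.4.2 and the 4.5-year ramped accrual in Section 11.3. It shows that the sponsor must choose; it does not make the present text consistent.

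A third reply is that the text is a harmless remnant of the original design. That may explain the synopsis and Section 11.1. Section 4.3, however, already carries the revised 54 months and 2.49 years beside the 4.5-year figure. The COVID-19 remark there only allows longer accrual, which widens the gap.

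**Conclusion.** The inconsistency is real and minor. Section 4.3's inputs imply about 5.0 years, not 4.5. The synopsis inputs imply a 4.0-year maximum and a 2.25-year mean. Section 11.1 implies a 2.75-year mean, and its 12-month close contradicts the 6-month rule elsewhere. These results are plain sums and need no modelling assumption.

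The 87.9% power and 520 events are right for 54-month ramped accrual plus 6 months. That check assumes exponential event times, the stated drop-out and cross-over accumulating over the study, and an unstated ramp-up count. The power loss in Step 3 is conditional on 4.5 years being a hard limit with 54-month accrual, and the documents do not say that it is.

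Section 8.3 adds a separate conflict. Follow-up ending on 15 December 2021 comes before the 50% accrual milestone of January 2022, so it fits none of these timelines.

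**What to change.** State one timeline and use it throughout.

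- **If the pattern in Sections 10.4.2 and 11.3 holds:** give the duration and maximum follow-up as about 5.0 years with a mean of 2.49 years in Section 4.3, the synopsis and Section 11.1. Replace the 3.5-year accrual in the last two, and change Section 11.1's 12-month close to 6 months.
- **If accrual is about 48 months:** keep 4.5 years and a mean of about 2.50 years. Correct the 54-month or 4.5-year accrual in Sections 4.3, 10.4.2 and 11.3, and align the accrual and closing text in the synopsis and Section 11.1.
- **If 4.5 years is binding with 54-month accrual:** restate power and expected events for that close.

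In the same edit, reconcile the 15 December 2021 date in Section 8.3 with the closing rule and the accrual milestones. Also check two figures that fit the original timeline: the 90% power in the synopsis and Section 5.2.1, and the enrolled fractions in Section 11.2.5 (24/42 = 57% and 18/42 = 43%).

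The cost is wording in a few sections. Either the stated maximum time on study becomes longer, or the stated accrual period shorter, or, in the third case only, the stated power lower.

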5.1. Informed Consent

Signed written informed consent forms, written in accordance with country-specific applicable data privacy acts, the Declaration of Helsinki, and the responsible central IRB, will be obtained from all patients prior to any study-related procedure.

The investigator or responsible staff will explain the nature, purpose and risks of the study and provide the patient with a copy of the patient informed consent form. The patient will be given sufficient time to consider the study's implications before deciding whether to participate.

Completion of the informed consent process can occur in-person and/or through remote encounters. Acceptable remote methods of consent include mailing, emailing, and/or faxing of consent documents and telephone or video contact with potential research subjects. REDCap and other 21CFR Part 11 capable and HIPAA compliant electronic data capture systems can be used for documentation of the informed consent process. Regardless of the method used, the informed consent process needs to ensure that all elements of informed consent are adhered to. The manner in which the informed consent process is completed should be fully documented and stored in study files.

Should there be any amendments to the protocol, such that would directly affect the patient's participation in the study (e.g. a change in any procedure), the informed consent form will be amended to incorporate this modification and the patient must agree to sign this amended form indicating that they re-consent to participate in the modified study.

A signed copy of the patient's informed consent form must be maintained in the study files. The patient's permanent medical records should indicate that the patient has been included in the study.

5.2. Study Population

The intended population for this study is patients with HFrEF and predominant CSA. Eligible subjects meeting inclusion/exclusion criteria will be considered for the study. Patients will be recruited from investigators' cardiology and sleep practices and from the institution's broad referral network.

5.2.1. Number of Patients

The hypothesized treatment effect is a 20% annual reduction in the primary endpoint (all-cause death, life-saving CV interventions, or hospitalization for worsening HF). This treatment effect is comparable to established therapies for the treatment of HF, such as renin-angiotensin system inhibitors, beta-blockers, and mineralocorticoid receptor antagonists. A total sample of 858 subjects (429 in each arm) achieves 90% power at a 5% significance level to detect a hazard ratio (HR) of 0.755, when the annual event rate in the control group is 40%, using a two-sided logrank test, assuming a 10% lost to follow-up rate and a 5% cross-over rate. (see Section 11.4 for Sample Size Calculation)

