Interim reports (open and closed) will be generated every 6 months (or more often as requested) including information on recruitment, baseline characteristics, data quality and availability, protocol deviations, and adverse events. Expected and actual number of randomized subjects and cumulative number of events will be reports and reviewed to ensure that recruitment is on target and the observed event rate is consistent with the assumed event rate.

At 18 months following randomization (or when approximately 43% of enrollment goal will be met), we will conduct a blinded sample size re-estimation using accumulating aggregate data to re-estimate nuisance parameters that have an impact on the power calculation of the trial. A comprehensive simulation study will be conducted to determine the impact of increasing the sample size and/or follow-up time on study power and overall type I error. The simulation study will be designed to mimic the LOFT trial as closely as possible and make use of the observed rate of early termination from the study and the overall event rates for all study participants, but will be blinded to the observed treatment arm-specific event rates and the difference between them. The overall observed event rate and its 95% confidence interval will provide a range of event rates that might be expected for the duration of the trial. The treatment arm specific event rate will be calculated based on the planned 20% reduction in 12-month event rate and the observed overall event rate. We will consider the following various scenarios including: 1) the originally planned study design; 2) additional year of follow-up after 858 participants are accrued. Additional scenarios may be included if deemed necessary upon discussion of the investigation team, the DSMB and the funding agency. The estimated power for different scenarios will inform the decisions on whether or not additional participants and/or follow-up time will be needed.

Interim comparative data will be considered confidential and will be available only to the DSMB members and to the DCC statistician/unblinded DCC staff analyzing the interim data and preparing the DSMB report. Concurrence with the monitoring plan by the Steering Committee, the DSMB, and the NIH will be required prior to implementation of the plan.

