We hypothesize a 20% reduction in the 1-year composite event rate, which is high enough to change practice. This effect is within the range of that observed across intervention studies (ranging from 35% for cardiac resynchronization therapy and beta blockers to 15% to 25% for other medications). We anticipate a 1-year event rate of 40% in the control group based on the HF literature showing that patients with advanced HF will experience annual morbidity and

mortality event rates of approximately 40% or greater, especially in the setting of co- morbid CSA.

A total sample of 858 subjects (429 in each arm) achieves 87.9% power at a 5% significance level to detect a hazard ratio (HR) of 0.755 when the 1-year event rate in the control group is 40%, using a two-sided logrank test. We assume a 5% cross-over throughout the study and 10% loss to follow-up throughout the study, and a Cox model with exponential distribution (assuming constant hazard rate), and a 2.49 average length of follow-up.

Original and Revised LOFT-HF Patient Accrual

	Original*	Revised ^{\$}		
Accrual end date	Jan 31, 2023		Jan 31, 2024	
Additional Follow-up Period	12 months	6 months	9 months	12 months
Average length of follow-up	2.75 years	2.49 years	2.74 years	2.98 years
Power	90.2%	87.9%	89.8%	90.4%

*: Corresponds to calculations provided in the original study protocol. Assumes the accrual pattern is uniform over 3.5 years.

\$: Based on the revised projected accrual pattern allowing a slower accrual during siteactivation.

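### The Synopsis and Section 5.2.1 state 90% power, but the protocol's own calculation for the adopted design gives 87.9%; the blinded re-estimation trigger still uses the old accrual timetable

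*Combined protocol and SAP*

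**What the plan says.** **Power.** Section 5.2.1 states: "A total sample of 858 subjects (429 in each arm) achieves 90% power at a 5% significance level", for a hazard ratio of 0.755, a 40% annual control event rate, 10% loss and 5% cross-over. The Synopsis gives the same power. For the derivation, 5.2.1 directs the reader: "see Section 11.4 for Sample Size Calculation".

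The power paragraph at the end of Section 11.2.5 says instead: "A total sample of 858 subjects (429 in each arm) achieves 87.9% power at a 5% significance level", with a "2.49 average length of follow-up". Section 11.3 says: "A total sample of 858 subjects (429 in each arm) achieves 88% power at a 5% significance level", assuming "an accrual period of 4.5 years with a slow ramp up until the end of May 2020" and a study that ends when the last patient has six months of follow-up. Section 4.3 describes the same design: "Patients will be followed up on average for a period of about 2.49 years", with a six-month minimum.

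The accrual table in 11.2.5 sets the versions side by side:

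| Design | Accrual ends | Further follow-up | Mean follow-up | Power |
|---|---|---|---|---|
| Original (uniform, 3.5 years) | Jan 2023 | 12 months | 2.75 y | 90.2% |
| Revised | Jan 2024 | 6 months | 2.49 y | 87.9% |
| Revised | Jan 2024 | 9 months | 2.74 y | 89.8% |
| Revised | Jan 2024 | 12 months | 2.98 y | 90.4% |

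**Re-estimation.** Section 11.2.5 schedules the blinded re-estimation thus: "At 18 months following randomization (or when approximately 43% of enrollment goal will be met"). Section 10.4.2 places 25% enrolment (n=215) in January 2021 and 50% (n=429) in January 2022.

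**End of follow-up.** Section 8.3 stops follow-up on 15 December 2021. Sections 10.4.2 and 11.3 plan accrual to January 2024, and 11.3 adds six months after that.

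**The concern.** The two places most readers consult for power give a figure that the statistics section does not support for the design in force. The cross-reference does not help them, because there is no Section 11.4; the calculation is in 11.3.

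The re-estimation trigger has a similar fault. Its two halves were one moment under the original accrual but no longer are. The re-estimation takes the pooled event rate with its 95% confidence interval and turns it into a range of power. The date therefore fixes how many events support that interval. A trigger that can be read as either of two dates, most of a year apart, leaves the precision of the exercise unspecified and the choice of date open.

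**Working it through.** **1. Reproducing the stated powers**

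Inputs (Sections 11.2.5 and 11.3): 429 per arm; control 1-year rate 40%; 20% relative reduction, so 32% on treatment; two-sided 5% log-rank; exponential times; 10% loss and 5% cross-over over the whole study.

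- Control hazard = −ln(0.60) = 0.5108 per year. Treated hazard = −ln(0.68) = 0.3857. Ratio = 0.755, as stated.
- Power comes from a Lakatos-type log-rank calculation with two-way cross-over.
- Original design: uniform over 42 months, plus 12.
- Revised design: August 2019 (54 months back from January 2024) with a linear ramp to end May 2020, then uniform to January 2024. The ramp's share, 7% of patients, is an assumption, chosen so that mean follow-up equals the stated 2.49 years.

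| Design | Events | Power recomputed | Power stated |
|---|---|---|---|
| Original, +12 months | 563 | 90.1% | 90.2% |
| Revised, +6 months (adopted) | 522 | 88.1% | 87.9% / 88% |
| Revised, +9 months | 555 | 89.9% | 89.8% |
| Revised, +12 months | 585 | 91.3% | 90.4% |

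Other start dates and ramp shapes put the adopted design between 88.1% and 88.8%. The 520 events expected in 11.2.5 match the adopted design (522), not the original (563). Type II error is 100 − 87.9 = 12.1%, against the 10% implied by the Synopsis and 5.2.1.

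**2. The re-estimation trigger**

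Original accrual: 18/42 = 42.9%, the printed 43%. In patients, 0.43 × 858 = 369.

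Current milestones, with month 18 counted from the start of enrolment. The start is either May 2019 (Section 10.4.1) or August 2019 (back-calculated).

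- Accrual rate from January 2021: (429 − 215)/12 = 17.8 per month.
- Extrapolating back eight months to end May 2020: 215 − 8 × 17.8 ≈ 72 patients.
- August start: month 18 is end January 2021, n=215, 25%. If the January 2021 milestone is read as 1 January, about 233 patients, 27%.
- May start: month 18 is end October 2020, n ≈ 72 + 5 × (215 − 72)/8 = 161, 19%.
- n=369 falls (369 − 215)/17.8 = 8.6 months after the January 2021 milestone. With that milestone at the end of January, this is month 26.6 (August start) or 29.6 (May start), a gap of 8.6 or 11.6 months. With 1 January and the August start the gap is 7.6 months.

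Expected pooled events, using the hazards above, 10% loss over the study and a linear ramp to 72. The 95% half-width of the log event rate is 1.96/√events:

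| Start | Events at month 18 | Half-width | Events at n=369 | Half-width |
|---|---|---|---|---|
| August 2019 | 46 | 0.29 | 114 | 0.18 |
| May 2019 | 32 | 0.35 | about 115 | 0.18 |

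**3. The same timetable elsewhere**

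- Section 11.2.5 puts the first look at month 24 with 57% enrolled: 24/42 = 57.1%. On the milestones, month 24 has about 31–38% enrolled, and the 156- and 312-event looks fall at about months 31 and 44 (August) or 34 and 47 (May), not 24 and 36.
- The Synopsis and 11.1 retain 3.5-year accrual, and 11.1 ends calls at the last patient's 12-month visit.
- Section 4.3 gives a 4.5-year total (54 months) beside about 54 months of enrolment plus 6, which is 60 months, or 57 if the 54 include the 3-month start-up.

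**4. Interaction with the December 2021 stop**

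If follow-up ends on 15 December 2021 and the last patient needs six months, randomisation ends about mid-June 2021. The milestones then give about 215 + 4.5 × 17.8 = 295 patients (34%), so n=369 would not be reached.

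**The case against.** The statistics section already prints the right power, shows original and revised designs together, and repeats 88% in 11.3; only two summary sentences lag, by 2.1 points. That is fair, and it limits the weight of the point. But 5.2.1 is where the sample size is justified, and its cross-reference leads nowhere.

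Section 5.2.1 names no accrual or follow-up period, and the revised 9- and 12-month columns also round to 90%. So its link to the original column is an inference, though a strong one. The contradiction does not depend on it: neither of those columns is the adopted six-month follow-up.

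The trigger's clock has no stated origin, and the ramp is not specified. This stands, which is why ranges are given. Under either start considered, the two halves are well apart.

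A reader might infer that the trigger date could change the decision to add patients or follow-up. With the planned pooled rate observed, a linear ramp and 11.2.5's 20%-reduction method, the lower end of the power range is about 76–78% at month 18 and 82% at 43% enrolled. But 11.2.5 sets no 80% threshold; the results only inform a discussion. Holding the hazard ratio at 0.755 instead gives about 83% at the August-start month-18 lower rate. The documents support a difference in precision, not a changed decision.

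**Conclusion.** The point holds as an internal contradiction. The 90% in the Synopsis and 5.2.1 is wrong for the adopted design, for which the protocol itself gives 87.9%. The gap is about 2 points, and both the original and the adopted figures reproduce, so this is an outdated statement, not a miscalculation. It should not be read as showing an inadequate sample size.

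The re-estimation trigger names two dates about 8–12 months apart, with roughly 32–46 pooled events at the first and about 115 at the second. Those figures rest on assumed start dates (May or August 2019), the assumed ramp and a clock from first enrolment.

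A reader might also infer that the interim looks are mistimed or their error control damaged. They are triggered by events, so only the projected calendar is out of date.

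All of this presumes that the January 2024 design is in force. If the December 2021 stop in Section 8.3 governs, neither 90% nor 87.9% describes the trial. The severity is should-fix.

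**What to change.** 1. **Reconcile the end of follow-up first.** State whether 15 December 2021 (Section 8.3) or six months after accrual to January 2024 (Sections 10.4.2 and 11.3) governs.
2. **If the January 2024 design governs:** replace 90% with 87.9% in the Synopsis and 5.2.1, labelled with accrual to January 2024, six months' follow-up of the last patient and mean follow-up of 2.49 years. Change the reference to Section 11.4 to 11.3. Define the re-estimation trigger by one quantity, either 369 randomised or a fixed pooled event count, and drop the 18 months.
3. **If December 2021 governs:** restate expected sample size, events and power for that date, and state whether and when the re-estimation still applies.
4. **Editorial:** update or remove the calendar months for the looks in 11.2.5; align the 3.5-year accrual (Synopsis, 11.1), the 12-month end rule (11.1) and the 4.5-year total (4.3) with the design that governs.

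Under the January 2024 design the cost is wording, and a stated power about 2 points lower; sample size, alpha, endpoint and monitoring boundaries stay as they are. Under the December 2021 stop, new projections are needed.
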